# 9. Assessments and procedures

Outcome data will be collected by research nurses, consultant and specialist physiotherapist, either in person during ventilation initiation appointment (baseline) or by postal, online or telephone questionnaire (baseline, 12 week visit). Data on survival will be collected up to a maximum of 108 weeks, through medical records. Data on adherence and ventilator effectiveness will be communicated through telemonitoring software to the Sheffield CTRU (control and intervention) and the clinical team (intervention arm only). Patient interaction with staff will be collected by the site on the intervention worksheets, which will form part of the process evaluation analysis.

In the instance of disparity between ventilator data and reported use from participants, the study ventilator data troubleshooting guide will be actioned.

The following windows are permitted for collection of follow up data. However, where these windows missed due to patient availability rather than an error at site, a protocol non-compliance will not be recorded.

- Baseline (day of initiation +/-3 days for questionnaires, and clinical tests within the last month, but not after initiation)
- Week 12 questionnaires +/- 7 days (between week 11,12,13)
- Week 12 oximetry +/- 7 days
- Survival
- NIV usage outcome windows specified in 8.2

Participant study data will be recorded on study-specific case report forms (CRFs) and patient questionnaires and then entered onto a remote web-based data capture system, transferring data to Sheffield CTRU for analysis. All aspects of data management will be provided by the Sheffield CTRU in accordance with their own standard operating procedures.

CTRU's in-house data management system (Prospect) used for the capture and storage of participant data, uses industry standard techniques to provide security, including password authentication and encryption. Access to Prospect is controlled by usernames and encrypted passwords, and a comprehensive privilege management feature can be used to ensure that users have access to only the minimum amount of data required to complete their tasks. Project-specific procedures for data management will be detailed in a data management protocol.

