# 4. Trial Design

DENIM is a multicentre, type 3 hybrid implementation-effectiveness, open-label, 1:1 stepped wedged, cluster-randomised controlled superiority trial of intensive monitoring and optimisation of non-invasive ventilation verses usual care. DENIM will recruit n=252 participants.

12 UK NHS sites will open recruitment for a roll-in period of six months. As sites are opening all patients will be recruited to receive the usual care delivered at that site. Following this, every three months thereafter, two sites each will receive training and all participants at that site will receive the

intervention until all sites have begun using the intervention (recruitment 24 months + final 3 months to allow follow-up, see flow diagram, figure 3). The maximum follow-period will be 27 months (108 weeks). The total duration of the trial is 41 months.

[figure not shown]

Figure 3. DENIM Trial flow diagram

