## **5.3 Target Healthcare Professionals**

DENIM will include healthcare professionals already working within the home ventilation service responsible for delivering NIV, typically physiotherapists or nurses. The wider MND team will be invited to shorter training to familiarise themselves with the intervention and trial procedures.

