## 6. Trial treatment

#### 6.1 Standard care

All sites commence the trial initiating patients in the usual manner. Local variation in site practice is allowed including some sites who have limited telemonitoring services but sites who have an established telemonitoring optimisation service (e.g. more than one preplanned/scheduled telemonitoring review per month) will be excluded. Sites who provide routinely more than two scheduled reviews with access to telemonitoring data within the first two weeks will also be excluded. Sites initiating in hospital but then do not provide more than two scheduled reviews within two weeks will be included.

Initiation location: initiation can occur at home, outpatients or in hospital.

Standard optimisation which is typically, for all patients, a scheduled follow-up telephone review without telemonitoring data at 2 weeks, face to face review at 12 weeks with/without blood gas measurements +/- NIV data downloads + ad hoc consultations triggered by the patient or staff (based on UK wide survey of practice and site consultations [21]).

Overnight oximetry: a limited number of sites use overnight oximetry as a measurement of NIV effectiveness, usually done once the patients used NIV for >4 hours but typically not routinely scheduled for all patients.

As an incentive, participants who are recruited to receive standard care will be signposted to a selection of patient resources (MND Association leaflets, www.mybreathing.mymnd.co.uk, DENIM website).

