## 8. Outcomes

Secondary patient outcomes can be completed at home in less than 10 minutes using a postal or online questionnaire, or if preferred telephone questionnaire. Baseline data is mostly that collected as part of usual care and will assess the severity, risk of death and risk of NIV ineffectiveness. Additional measures collected at baseline aim to describe the potential factors influencing NIV effectiveness e.g. bulbar dysfunction and home situation. The digital healthcare literacy scale[52] is a three-item scale that can be used to identify those likely to need additional support to use technology.

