#### Key:

- ☑ Questionnaire/CRF completed on paper and returned via post
- Questionnaire/CRF completed over the telephone with local study team
- Questionnaire/CRF completed online

X assessment in clinic

- data collected from ventilator telemonitoring system
- \*NIV adherence is collected as per the ventilator standard operating procedures. The exact procedure may differ between ventilator manufactures, please refer to study specific 'ventilator SOPs' for more guidance.

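### The protocol does not stop staff who deliver a patient's NIV care from taking that patient's week-12 questionnaire answers by telephone

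*Protocol*

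**What the plan says.** Section 4 of the protocol describes the trial as "open-label, 1:1 stepped wedged, cluster-randomised controlled superiority trial". Section 9 names the collectors: "Outcome data will be collected by research nurses, consultant and specialist physiotherapist". For the later questionnaires it allows collection "by postal, online or telephone questionnaire (baseline, 12 week visit"), with a window of seven days either side of week 12. The key to Table 2 defines the telephone option as "Questionnaire/CRF completed over the telephone with local study team". Section 8 says patients can complete the secondary outcomes at home "using a postal or online questionnaire, or if preferred telephone questionnaire".

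Section 5.3 says the trial's target staff are "healthcare professionals already working within the home ventilation service responsible for delivering NIV, typically physiotherapists or nurses". Section 6.2.2 schedules their contacts in the intervention phase at days 2, 5 and 10 and weeks 2, 3, 4, 8 and 12. Section 6.2.6 expects most or all of this added contact to be by telephone. Section 6.1 describes typical usual care as one telephone review at week 2 and a "face to face review at 12 weeks with/without blood gas measurements". Section 11.3 takes QALYs from the EQ-5D-5L at weeks 0 and 12.

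**The concern.** Dyspnoea-12, McGill, S3NIV and EQ-5D are the patient's own judgements, and both patient and staff know the phase. A patient answering aloud to the clinician who supports their ventilation may give kinder answers than on paper or to a stranger. S3NIV is the most exposed, because it asks about symptoms and side effects of the very treatment that clinician manages.

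If such an effect is stronger where staff have had more contact with the patient, it adds to the intervention contrast and cannot be separated from a real benefit. It would affect the secondary patient-reported outcomes and, through EQ-5D, the within-trial cost per QALY. If mode and collector are not recorded, the extent of the practice cannot be described afterwards.

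**Working it through.** The protocol gives no figure to reproduce here, so the check sets the sections side by side.

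1. **Can treating staff be collectors?** Section 9 lists a consultant and a specialist physiotherapist. The phrase could mean a medical consultant, or physiotherapists of consultant and specialist grade. Either way it includes physiotherapists, one of the two professions that section 5.3 names as delivering NIV. Section 5.4 has a member of the patient's own care team identify and consent participants, so care staff already carry out trial tasks.

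2. **Can they take the week-12 questionnaires?** The telephone option in the Table 2 key is with the local team, so the caller comes from the site and is not central or masked. No section bars staff who deliver a patient's NIV from making that call.

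3. **Is contact equal between phases?** Scheduled contacts after initiation:
   - intervention: 3 (days 2, 5, 10) + 5 (weeks 2, 3, 4, 8, 12) = 8, of which 7 precede week 12;
   - typical usual care: 2 (weeks 2 and 12), of which 1 precedes week 12.

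   The questionnaire window is weeks 11 to 13, so the week-12 intervention contact falls inside it. So does the typical usual-care review at week 12. The asymmetry is therefore in the amount of earlier contact, and in the goal-setting and coaching training of section 6.2.1. It is not the presence or absence of a clinician at week 12.

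4. **Do permitted questionnaire modes differ by phase?** No. Table 2 gives the four instruments the same set of post, telephone and online symbols at week 12, without reference to phase.

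5. **How large could it be?** Let p be the share of patients whose answers are taken by telephone by treating staff, and d the mean favourable shift in SD units that this causes. The spurious difference is p(intervention) × d(intervention) − p(control) × d(control). The documents give neither p nor d. By way of illustration, on assumed values only:
   - p = 0.5 in both phases and the same d in both: 0.5d − 0.5d = 0;
   - p = 0.5 in both phases, d = 0 in control and 0.1 to 0.3 in intervention: 0.5 × 0.1 = 0.05 SD to 0.5 × 0.3 = 0.15 SD;
   - p = 0 in both phases: 0.

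   The result runs from nothing to a modest shift, depending wholly on the assumptions.

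**The case against.** The strongest reply is that the protocol already leans the right way. Section 8 puts post or online first and leaves telephone to the patient's preference, and research nurses are on the collector list. The section 9 list covers all outcome data, including what is gathered in person at baseline, and does not assign consultants or physiotherapists to telephone questionnaires. Elsewhere the protocol distinguishes clinical from research teams (sections 5.4 and 5.5), so the local study team need not be the treating team. Section 6.2.7 lets clinical need drive patient contact, so eight contacts is the schedule and not necessarily what is delivered. Open-label reporting of subjective scores is also inherent in the design and would remain under self-completion.

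All of this stands, and it limits the point to what the text permits, not what it prescribes. It does not supply the missing rule: a site could follow the protocol exactly and still have treating staff take these answers.

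A reader might go further and infer that questionnaires are taken by telephone in the intervention phase and face to face in usual care. The documents do not support that. The telephone and face-to-face contrast in sections 6.1 and 6.2 concerns clinical reviews. The permitted week-12 questionnaire modes are identical, and section 6.2 defines the intervention as an addition to usual care, so the face-to-face review at week 12 is not said to be dropped.

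**Conclusion.** The point holds as a low-cost improvement. The protocol leaves open that staff delivering NIV and the intervention collect week-12 patient-reported outcomes from their own patients, and the heavier contact schedule in the intervention phase gives a plausible direction of bias towards the intervention.

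The size cannot be derived. It depends on telephone uptake, on who makes the calls and on the strength of any interviewer effect, none of which is documented. A reader might want to turn this into an inflated false-positive rate. That would require stacking assumed uptake on an assumed shift, and borrowing for the questionnaires the intra-cluster correlation of 0.05 that section 11.1 gives only for days of NIV use. The documents do not support such a figure.

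The primary outcome is downloaded from the ventilator and is untouched. What is at stake is the credibility of the secondary patient-reported outcomes and the EQ-5D-based QALYs.

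**What to change.** In section 9 and the Table 2 key:

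- keep post or online self-completion first, in line with section 8;
- state that any telephone questionnaire is taken by a research nurse or other listed study team member with no part in that patient's NIV reviews, on a call separate from the week-12 clinical review, and that this applies in both phases;
- add two CRF items, mode of completion and role of the collector.

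Telephone access stays available to patients who need it, and clinical care is unchanged. The cost is a little wording, two tick-boxes and minor scheduling at sites. No new staff are needed, because research nurses are already named as collectors.

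A sensitivity analysis restricted to self-completed forms is not recommended. Mode is chosen after baseline and is plausibly linked to disability, so the restriction would introduce selection and would not isolate the interviewer effect.

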#### Key:

- ☑ Questionnaire/CRF completed on paper and returned via post
- Questionnaire/CRF completed over the telephone with local study team
- Questionnaire/CRF completed online

X assessment in clinic

- data collected from ventilator telemonitoring system
- \*NIV adherence is collected as per the ventilator standard operating procedures. The exact procedure may differ between ventilator manufactures, please refer to study specific 'ventilator SOPs' for more guidance.

## 9.2 Unscheduled visits

For participants in the intervention arm, pages in the workbook for unscheduled visits will be provided to capture ad hoc visits outside of the intervention schedule.

#### 9.3 Participant withdrawals

Participants may wish to withdraw from the study or study treatment, or there may be a clinical need to withdraw the participant.

Participants may withdraw their consent for the study at any time, without providing a reason for this. If this occurs, this will be documented on a study completion/ discontinuation form and the patient

notes, and no further data will be collected for this participant for the study. Although the participant is not required to give a reason for discontinuing their study treatment, a reasonable effort will be made to establish this reason while fully respecting the participants' rights. Any data collected up to the point of the participant's withdrawal will be retained, and used in the final analysis, and this is made clear to the patient at the time of consent.

Participants who undergo a switch to tracheostomy ventilation will be withdrawn from the intervention but will be encouraged to continue to provide data at 12 weeks and survival outcomes.

Participants whose capacity to give informed consent to continue in the study is impaired or uncertain during the trial (typically due to impaired communication or the development of dementia) will continue in the trial, as long as they indicate assent through a personal consultee and have expressed no desire to withdraw. If the trial team become aware that a participant has lost capacity to consent, a personal consultee (i.e. family member or friend) will be identified from their care records, if not already known to the team. The patient's clinical care team will confirm consent to contact, and the family member/friend will be sent a personal consultee pack to confirm that they believe the patient would wish to continue participation.

Excessive participant withdrawal from follow-up has a negative impact on a study. Sites will explain the importance of remaining on study follow-up to participants, and that changes to planned treatment need not imply withdrawal from the study. Centres will explain the options for withdrawal:

- Withdrawal from the DENIM intervention only, i.e. no further intervention delivery visits but the
  participant remains in the trial. Participants who decide to no longer use NIV and/or receive
  enhanced support will be encouraged to continue with the trial for data collection purposes
  and will be switched to receive usual care which allows them to retry NIV at a later date
  (without re-entry into the study).
- Withdrawal from the DENIM intervention and all but essential data collection, i.e. survival status / cause of death, and routine data from hospital notes +/- ventilation data
- Withdrawal from the DENIM trial entirely. Unless specified by the participant, all data collected up to this point will be used in the analysis and no further intervention or research visits will be conducted.

Participants who wish to withdraw from the interview component of the study will have their interview data withdrawn, as long as they inform the team of this within 4 weeks of their interview. After this time has passed, data analysis will have begun, and it will not be possible to remove their data. This will be made clear to participants in the Information Sheet.

## 9.4 Loss to follow-up

Participants will be defined as lost to follow up only if no data can be collected at the study close. If a participant is lost to follow up, this will be recorded in the CRF using the study completion/discontinuation form.

# 10. Safety Reporting

ICH-GCP requires that both investigators and sponsors follow specific procedures when reporting adverse events in clinical studies. These procedures are described in this section.

## 10.1 Definitions

Table 3. Adverse event definitions

Term	Definition
Adverse Event (AE)	Any untoward medical occurrence in a study participant. (refer to SOP PM004 Adverse Events and Serious Adverse Events for more details)
Unexpected AE/SAE	An adverse event or serious adverse event which has not been pre-specified as expected.
Serious Adverse Event (SAE)	An AE which is serious, defined as any untoward medical occurrence or effect that:  Results in death Is life-threatening* Requires hospitalisation or prolongation of existing inpatients' hospitalisation** Results in persistent or significant disability or incapacity Is a congenital anomaly/birth defect Is otherwise considered medically significant by the investigator***
Related AE/SAE	An AE or SAE which is related to a research procedure

Notable Event	An event of particular interest that does not necessarily meet
	the criteria for seriousness but requires expedited reporting as
	per the protocol.

\*The term life-threatening in the definition of a serious event refers to an event in which the patient is at risk of death at the time of the event; it does not refer to an event that hypothetically might cause death if it were more severe, for example, a silent myocardial infarction.

## 10.2 Recording and reporting

AEs and SAEs are defined as an event that occurs after the patient has provided written informed consent for trial entry and within the 12 week follow up period. Only AEs related to the trial or trial processes will be recorded.

AEs will be recorded on the adverse event report form, within the participant CRF, including those that fulfil the criteria for being serious (see section 10.1). Sites are asked to enter all available information onto the study database as soon as possible after the site becomes aware of the event.

SAEs will require more detailed information to be recorded. In such cases, the event must also be reported to the Sheffield CTRU within 24 hours of the site becoming aware of the event. The CTRU will notify the Sponsor of these events through monthly reports.

## 10.3 Study specific exemptions

Adverse events related to the normal disease progression of MND will NOT be recorded. These include:

- Respiratory system: dyspnoea, respiratory failure, pneumonia
- Thrombotic events
- Gastro-intestinal: dysphagia, constipation
- General condition: accidental injury (fall related trauma) aggravated condition
- Muscular weakness
- Gastrostomy or complications of gastrostomy insertion
- Tracheostomy (this would be an indication for withdrawal)

\*\*Hospitalisation is defined as an inpatient admission, regardless of length of stay, even if the hospitalisation is a precautionary measure for continued observation. Hospitalisations for a pre-existing condition, that has not worsened or for an elective procedure do not constitute an SAE.

\*\*\*Other important medical events that may not result in death, be life-threatening, or require hospitalisation may be considered a serious adverse event/experience when, based upon appropriate medical judgement, they may jeopardise the patient and may require medical or surgical intervention to prevent one of the outcomes listed in this definition.

Adverse events collected on the case report forms will not be recorded on the AE log. These include:

- death
- botulinium toxin injections
- admission to hospital for problems unrelated to respiratory insufficiency or unrelated to MND (except ICU/HDU admissions which should be recorded)

Adverse events judged by site to be unrelated to MND or the study procedures will not be recorded on the AE log.

## 10.4 SAE notification procedure

Site staff will be responsible for reporting all SAEs. Once an SAE has been identified, a member of the site research team will complete an SAE form, notifying the site's PI and send this to the CTRU.

All SAE forms must be sent by fax to [name] or email to [contact]. Receipt of the initial report should be confirmed within one working day. The site research team should contact the study team at CTRU if confirmation of receipt is not received within one working day.

SAEs which are related and unexpected will be reported to the sponsor and we will expedite these to the Research Ethics Committee (REC) within 15 days of becoming aware.

#### 10.5 CTRU responsibilities

The Sponsor usually delegates CTRU responsibility for the reporting of SAEs to the regulatory authorities and the research ethics committee, as appropriate. CTRU will also keep all investigators informed of any safety issues that arise during the course of the study.

## 10.6 SAE additional reporting

The DMEC and TSC will also receive information on all AEs and SAEs, at a frequency agreed with each committee and documented in the appropriate charter/terms of reference.

## 11. Statistics

#### 11.1 Sample size

The primary outcome is the number of days in which patients use NIV for >4hr, assuming standard deviation of ten0 days with a high skew. A modest change in survival and quality of life requires a large change in adherence; we assume a mean difference of six days to reflect this. Assuming a

conservative estimate where each site recruits, on average one patient per month in months 7-24 and three patients in the six months roll in period this will recruit a total of 252 patients. Allowing for 15% drop-out, 214 participants provide 90% power to detect an increase of six days in adherence assuming an inter-cluster coefficient of 0.05 and a two-sided 5% significance level. The sample size was calculated using a modified version of the Stata stepped wedge macro which allowed non-integer number recruited per step.

